## 6 Analysis Sets

Safety Analysis Set: The Safety Analysis Set will consist of all enrolled subjects who have undergone insertion of the NUVISION™ NAV Ultrasound catheter.

**Per Protocol (PP) Analysis Set**: The PP Analysis Set will include all enrolled subjects who met the study eligibility criteria and in whom assessments were performed with the NUVISION™ NAV Ultrasound catheter.

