Study Population	
Subjects who are scheduled to undergo an imaging process during an interventional cardiac ablation procedure for management of the following:
 
 Scar-related Atrial Tachycardia (AT; includes atypical atrial flutter), procedures resulting from previous atrial fibrillation ablation; Persistent Atrial Fibrillation (PsAF); Paroxysmal Atrial Fibrillation (PAF); Ventricular Tachycardia (VT): ischemic and non-ischemic VT, cardiomyopathy and idiopathic VT; Premature Ventricular Complex (PVC);
Sample Size	Up to 30 subjects will be enrolled in the study.
Geographic areas to be included	Europe and Israel
Study Duration	Approximately 5 months enrollment and 7-day follow-up per subject.
Visit Intervals	Baseline/procedure, 7-day follow-up phone call or clinic visit after study procedure
Procedure(s) description	During study procedures, investigators will use the investigational catheter instead of the institution's standard ultrasound catheter (e.g. SOUNDSTAR™ ultrasound catheter).

	
The use of the investigational catheter is mandatory for thrombus detection, imaging for volume measurements, during transseptal puncture and as navigational ultrasound (ULS) catheter throughout the procedure.
 
Any use of a non-investigational ultrasound device will be considered a failure of the primary effectiveness endpoint.

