9.2 Participant Exclusion Criteria

Candidates will be excluded if ANY of the following criteria apply:

1. Structural heart defect which can only be repaired by cardiac surgery
2. Pericarditis within 6 months
3. LVEF \leq 25% for VT patients
4. LVEF \leq 40% for patients with atrial arrhythmia
5. History of chronic gastro-intestinal medical problems involving the esophagus, stomach and/or untreated acid reflux
6. History of abnormal bleeding and/or clotting disorder.
7. Clinically significant infection or sepsis
8. History of stroke or TIA within the past 6 months of enrollment
9. Uncontrolled heart failure or NYHA function class IV
10. Implanted with a pacemaker or intracardiac cardiac defibrillator within the past 6 weeks (42 days)
11. Implanted with a mechanical valve
12. Diagnosed atrial or ventricular myxoma, interatrial baffle or patch, tumor or other abnormality that precludes catheter introduction or manipulation.

13. Any of the following within 6 months of enrollment
 - a) Major surgery except for the index procedure
 - b) Myocardial infarction
 - c) Unstable angina
 - d) Percutaneous coronary intervention (e.g. CABG or PTCA)
14. Patients with any other significant uncontrolled or unstable medical condition (such as uncontrolled bradyarrhythmia's, ventricular arrhythmias, hyperthyroidism, or significant coagulation disorder)
15. Significant congenital anomaly or medical problem that in the opinion of the investigator would preclude enrollment in this study.
16. Women who are pregnant (as evidenced by pregnancy test if pre-menopausal), lactating, or who are of childbearing age and plan on becoming pregnant during the course of the clinical investigation.
17. Categorized as vulnerable population and requires special treatment with respect to safeguards of well-being.
18. Concurrent enrollment in an investigational study evaluating another device or drug.

10. Participant Withdrawal or Termination

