10.3 Subject Disposition

- **Enrolled Subjects:** Patients who sign the ICF.
- **Excluded Subjects:** Subjects who are enrolled but never undergo insertion of the study catheter. Excluded subjects will be subjected to safety event reporting between ICF signature and date of exclusion. Subjects who signed the ICF but are found to be ineligible prior to insertion of the catheter are also considered as excluded.
- **Discontinued Subjects:** Enrolled subjects who have the study catheter inserted but no assessments are performed with it. Discontinued subjects will remain in follow-up for 7 days for safety evaluation.
- **Lost to Follow-up Subjects:** Enrolled subjects of which contact is lost after most recent visit (despite 3 documented attempts to contact the subject).
- **Withdrawn / Early Termination Subjects:** Subjects who withdraw consent for study participation or are withdrawn by the investigator, are terminated from the study prior to completion of all follow-up visits.
- **Completed Subjects:** Enrolled subjects who have not been excluded, discontinued, withdrawn, terminated early, or lost-to-follow-up from the study prior to the final study visit.

11. Responsibilities

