14.2.2 Study Procedure

Subjects will arrive to the electrophysiology laboratory for their study procedure and will undergo preparation for the procedure per the hospital's standard protocol (discretion of investigator)

Overall Use of the Investigational Device

During study procedures, investigators will use the investigational catheter instead of the institution's standard ultrasound catheter choice (e.g. SOUNDSTAR™). Any use of a non-investigational ultrasound device will be considered a failure of the primary performance endpoint.

The use of the investigational NUVISION™ NAV Ultrasound Catheter is **mandatory** for:

- Thrombus detection and LA/LV imaging for volume measurement at the start of the procedure;
- During transeptal puncture;
- And as navigational ULS catheter throughout the procedure.

Imaging guidance for LA/LV volume measurements:

- Capture preferably the full chamber in one ULS volumetric segment, if needed several segments can be taken.
- For capturing of the LA:
 - Capture 4D ULS clip (full 90°x90°) of the LA (with PVs and LAA) taken from the RA.
 - Repeat the acquisition from 3-6 slightly different positions, where the LA volume is partial.
Note: Capture 4D ULS clip before transeptal and insertion of any other catheters to the LA, by using the default ULS settings, and without using the "zoom" function.
 - Place the investigational NUVISION™ NAV Ultrasound Catheter near the interatrial septum and make sure to capture the ENTIRE left atrium.
 - Confirm by seeing both anterior-posterior and Roof to Mitral valve planes.
 - Make sure to allow sufficient ULS depth by visualizing the distal LAA.
- For capturing of the LV:
 - The catheter can be positioned either in the RA near the inferior septum or in the right ventricle (RV) near the interventricular septum.
 - Make sure to allow sufficient ULS depth by visualizing the entire chamber from the Mitral valve to the distal apex.

Investigators should use the CARTO™ 3 system to **"bookmark"** instances of abnormal study catheter "imaging noises". This will allow for further analysis of the data.

Standard of Care Ablation Procedure

Treatment will be per institution's standard of care (SOC).

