20.3 Analysis Sets

Safety Analysis Set: The Safety Analysis Set will consist of all enrolled subjects who have undergone insertion of the NUVISION™ NAV Ultrasound catheter.

Per Protocol (PP) Analysis Set: The PP Analysis Set will include all enrolled subjects who met the study eligibility criteria and in whom assessments were performed with the NUVISION™ NAV Ultrasound catheter.

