## 8.5 Analysis of Primary Endpoint(s)

Primary Safety Endpoint is defined as the occurrence of serious adverse events related to the Investigational catheter within 7 days of index procedure. An SAE will be counted as related to the investigational catheter if the relationship to a study catheter is anything other than 'Not Related'.

The number of subjects with SAEs related to the investigational catheter will be summarized in the Safety Analysis Set overall and per procedure type (atrial ablation/ventricular ablation) by System Organ Class and Preferred Term and level of relationship. All tables will present summaries both by subject and by event. If a subject has multiple occurrences of an event within a level of summarization, then for the by-subject summaries only a single occurrence will be counted at each level of summarization at the highest level of severity/relationship; for the by-event summary all events will be counted.

All investigational catheter related SAEs will be listed by System Organ Class and Preferred Term, severity, causality (defined as possible, probable or having a causal relationship to the device and/or procedure), anticipation and outcome.

Primary Performance Endpoint is defined as the completion of imaging required for the study procedure with the NUVISION™ NAV Ultrasound Catheter without resort to non-study ultrasound device(s).

The number of subjects who successfully completed the procedure without resort to a non-study ultrasound device will be summarized overall and per procedure type (atrial ablation/ventricular ablation) for the PP Analysis Set.

A listing of the primary performance endpoint will be provided.

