## 8.7 Analysis of Additional Endpoint(s)

Additional Procedural Data will be analyzed overall and per procedure type (atrial ablation/ventricular ablation) using the PP Analysis Set and include the following parameters:

- Whether Imaging for Left Atrium (LA) and Left Ventricle (LV) volume measurements was done;

- Total fluoroscopy time;
- Total duration of the procedure.

For each of the above procedural data, the denominator will be the number of subjects where assessments with the study device are performed. Listings will be provided.

Additional safety data, e.g., all non-serious AEs not related to the investigational catheter will be listed by System Organ Class and Preferred Term, severity, causality (defined as possible, probable or having a causal relationship to the device and/or procedure), anticipation and outcome.

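### Primary performance is summarised only in a per-protocol set whose undated eligibility condition can remove subjects after their catheter outcome is known

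*SAP*

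**What the plan says.** Protocol 14.2.2 scores the endpoint without any condition on the subject: "Any use of a non-investigational ultrasound device will be considered a failure of the primary performance endpoint". The protocol synopsis carries the same rule.

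Who is counted is settled elsewhere. SAP 8.5 states that the number of successes "will be summarized overall and per procedure type (atrial ablation/ventricular ablation) for the PP Analysis Set", and Protocol 20.4.6 assigns the same set. SAP 6 defines that set as "all enrolled subjects who met the study eligibility criteria and in whom assessments were performed" with the study catheter; Protocol 20.3 uses the same wording. The Safety set, which is every enrolled subject with the catheter inserted, is not used for performance.

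The handling of ineligible subjects is described only up to insertion. Protocol 10.2 allows them to be replaced if ineligibility is found before that point, and Protocol 10.3 classes them as excluded: "Subjects who signed the ICF but are found to be ineligible prior to insertion of the catheter are also considered as excluded". No disposition category covers ineligibility found after insertion.

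**The concern.** Whether the catheter completed the required imaging is a fact about the procedure, and a later finding that the subject should not have been enrolled does not change it. The PP definition nevertheless lets that finding remove the result. It fixes no date for the judgement, names no one to make it and does not limit the information used. The study is open-label, so whoever makes the judgement can already know whether another ultrasound device was needed.

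At stake is one of only two primary endpoints in a first-in-human study of about 30 subjects. With no hypothesis test or success threshold, the reported proportion is itself the result. The endpoint is also split by procedure type (SAP 8.5) and by five arrhythmia subgroups (SAP 8.9), where one removal weighs more.

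**Working it through.** **Step 1: on whom does the eligibility condition act?** PP has two conditions: eligible, and assessed with the study catheter.

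| Subject | Assessed with catheter? | In PP without the eligibility condition? | In PP as written? |
|---|---|---|---|
| Ineligible, found before insertion | No | No | No |
| Eligible, imaged | Yes | Yes | Yes |
| Ineligible, found after imaging | Yes | Yes | No |

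Only the third row changes. The condition therefore has an effect only once a performance outcome exists. The documents foresee such subjects: Protocol 17 gives departure from the inclusion and exclusion criteria as an example of a deviation, and SAP 8.2 counts subjects who fail the criteria. Subjects with insertion but no assessments fail the second condition; that is a separate matter.

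**Step 2: direction.** Let n be the subjects imaged, f the failures, and r_f and r_s the failures and successes removed as ineligible.

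- All imaged: (n − f)/n
- PP: (n − f − r_s)/(n − r_f − r_s)

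The PP rate is the higher one exactly when r_f/(r_f + r_s) > f/n, that is, when failures are over-represented among those removed. It is lower when they are under-represented.

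**Step 3: size.** The plan has no figure to reproduce. The 30 subjects in SAP 7 rest on previous experience, with no assumed success rate or precision. I assume that all 30 are imaged, and use exact (Clopper-Pearson) intervals at the two-sided 95% level in SAP 5. SAP 8.5 does not itself ask for an interval on this endpoint, so the intervals are my illustration. When all n succeed, the lower limit is 0.025^(1/n); for n = 29 this is 0.881.

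| Failures among 30 | All imaged | PP, every failure removed |
|---|---|---|
| 1 | 29/30 = 96.7% (82.8 to 99.9) | 29/29 = 100% (88.1 to 100) |
| 2 | 28/30 = 93.3% (77.9 to 99.2) | 28/28 = 100% (87.7 to 100) |
| 3 | 27/30 = 90.0% (73.5 to 97.9) | 27/27 = 100% (87.2 to 100) |

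Partial removal lies between: with three failures, removing one gives 27/29 = 93.1% and removing two gives 27/28 = 96.4%.

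In the other direction, with two failures, removing one ineligible success gives 27/29 = 93.1% against 28/30 = 93.3%. A removed success thus costs about 0.2 points, whereas removing one of the two failures (28/29 = 96.6%) adds about 3.2 points.

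In an assumed procedure-type stratum of 10 with one failure, 9/10 = 90.0% (55.5 to 99.7) becomes 9/9 = 100% (66.4 to 100).

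**The case against.** The strongest reply is that an eligibility condition is an ordinary part of a PP definition and that the documents place eligibility before the procedure. Subjects are prescreened (Protocol 6.4.2), several criteria are dated to enrollment (9.2), LVEF is re-checked before insertion when imaging is older than 6 months, and a cardiac CT of the anatomy is required beforehand (14.2.1). Waivers are prohibited (17). SAP 8.2 will show how many subjects fail the criteria and the size of each set, and SAP 8.5 provides a listing. The analysis is descriptive and no effectiveness claims will be made. This makes late-found ineligibility less likely and partly visible. It does not put a cut-off in the PP definition or return a removed failure to the rate. The population for the listing is not stated, and nothing requires removed subjects to be shown with their outcomes.

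Four stronger readings are tempting, and the documents do not support them.

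- *Protocol against SAP.* Both documents carry the same PP definition and use. Protocol 14.2.2 defines a failure; Protocol 20.3 defines who is analysed. These do not contradict each other.
- *Exclusion criterion 12 is itself catheter manipulability.* Its closing words, "tumor or other abnormality that precludes catheter introduction or manipulation", may suggest so, but the criterion opens by requiring a diagnosed abnormality of the patient. Difficulty in handling the catheter does not meet it. Criterion 15, which rests on investigator opinion, refers to enrollment, and Protocol 21.2.1 places enrollment at consent signature.
- *SAP 8.7 contradicts SAP 6.* Its sentence "the denominator will be the number of subjects where assessments with the study device are performed" has no eligibility condition, but the section first assigns those data to the PP set, so the sentence can be read as applying within PP.
- *The rate is necessarily inflated.* Step 2 shows that the direction depends on who is removed.

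**Conclusion.** The concern holds as a gap shared by both documents. The primary performance rate is confined to a set whose eligibility condition can remove only subjects already imaged, at no stated time and with the outcome open, and no summary of all imaged subjects stands beside it. That leaves a route for outcome-dependent exclusion; it does not show that the route would be used.

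The size is illustrative. With 30 imaged subjects, each single failure removed raises the reported rate by roughly 3 points, and removing the only failure yields a reported 100%. This assumes that the failure falls in a subject later judged ineligible. The documents give neither an expected failure rate nor a rate of late-found ineligibility; if no imaged subject is found ineligible, the two rates are identical.

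**What to change.** In SAP 8.5, and in Protocol 20.4.6 when it is next amended:

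1. Report the primary performance endpoint for all subjects imaged with the study catheter, regardless of ineligibility found later. At minimum, present this alongside the PP result, overall and by procedure type.
2. State in SAP 6 (and Protocol 20.3 at the same amendment) that PP eligibility is judged only from information recorded before catheter insertion.
3. List each imaged subject left out of PP, with the reason and the performance outcome.

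The cost is a few sentences, one further summary and one listing, all from data already collected. The SAP change can come first; the protocol wording needs the amendment approvals described in Protocol 17, which is why it can wait for the next amendment. The downside for the sponsor is a success rate that may be slightly less favourable.

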## 7 Sample Size Justification

A sample size of 30 subjects will be enrolled to characterize the performance and safety of the Investigational catheter.

The sample size is selected based on previous experience with similar design in first in human assessments of multi-electrode mapping catheters. This study is meant to characterize the catheter's ability to perform safely in various types of arrhythmias. No clinical claims of effectiveness or patient outcomes will be made from this study.

## 8 Statistical Analysis Methods

#### 8.1 General Conventions

SAS® version 9.4 or higher will be used for all analysis. Standard descriptive summaries for continuous data include the number of observations with data, number of observations with missing data, mean, standard deviation, median, minimum, and maximum values. For categorical data, the count and percentage will be provided. Percentages will be based on the number of subjects without missing data.

## 8.2 Disposition of Study Subjects

Subject disposition will be summarized and listed for the subject categories defined in protocol section 10.3 for all subjects. Subject disposition will be summarized using categorical summaries. The number and percent of patients who are enrolled in the study, fail inclusion/exclusion criteria, are included in the safety, and perprotocol analysis sets, complete the study, and prematurely discontinue from the study will be presented. Patients who are prematurely discontinued will be summarized by primary reason for discontinuation.

## 8.3 Demographic and Baseline Characteristics

Demographic variables will include age and sex. Baseline characteristics will include the primary study arrhythmia/procedure and the number of previous ablation procedures. All demographic and baseline characteristics will be summarized using categorical and continuous summaries, as appropriate, for the Safety Analysis Set. A listing of subject demographic and baseline characteristics will be generated.

Medical history will be presented using the Safety Analysis Set.

Cardiovascular (CV) and Thromboembolic/Cerebrovascular medical history will be collected and summarized using categorical summaries. Each subject will be

counted once under each type of CV and/or thromboembolic/cerebrovascular medical history they have experienced.

The number of subjects with TTE performed and those with pericardial effusion will be presented using categorical summaries. The left ventricle ejection fraction and the maximum dimension of pericardial effusion will be presented in continuous summaries.

The number of subjects with an exam performed to assess the presence of thrombus and whether a thrombus is present will be summarized.

Other medical history, including NYHA class, occurrence of diabetes, and history of bleeding will be summarized similarly.

## 8.4 Endpoint(s) and Associated Hypotheses

## 8.4.1 **Primary Endpoint(s)**

Safety: Occurrence of serious adverse events within 7 days of index procedure related to the NUVISION™ NAV Ultrasound Catheter

**Performance**: Completion of imaging required for the study procedure with the NUVISION™ NAV Ultrasound Catheter without resort to a non-study ultrasound device

## 8.4.2 Secondary Endpoints

Physician assessment of deployment, maneuverability, navigational features and imaging quality acquired with the NUVISION™ NAV Ultrasound Catheter during the study procedures

Occurrence of all other serious adverse events within 7 days of index procedure (not related to the NUVISION™ NAV Ultrasound Catheter)

Occurrence of non-serious adverse events within 7 days of index procedure related to the NUVISION™ NAV Ultrasound Catheter

## 8.4.3 Additional Endpoints

Additional Procedural data, including:

- Anatomical structures assessed

- Whether imaging for Left Atrium (LA) and Left Ventricle (LV) volume measurements was done

- Total fluoroscopy time
- Total procedure duration

Additional safety data: All non-serious AEs not related to the investigational catheter

## 8.5 Analysis of Primary Endpoint(s)

Primary Safety Endpoint is defined as the occurrence of serious adverse events related to the Investigational catheter within 7 days of index procedure. An SAE will be counted as related to the investigational catheter if the relationship to a study catheter is anything other than 'Not Related'.

The number of subjects with SAEs related to the investigational catheter will be summarized in the Safety Analysis Set overall and per procedure type (atrial ablation/ventricular ablation) by System Organ Class and Preferred Term and level of relationship. All tables will present summaries both by subject and by event. If a subject has multiple occurrences of an event within a level of summarization, then for the by-subject summaries only a single occurrence will be counted at each level of summarization at the highest level of severity/relationship; for the by-event summary all events will be counted.

All investigational catheter related SAEs will be listed by System Organ Class and Preferred Term, severity, causality (defined as possible, probable or having a causal relationship to the device and/or procedure), anticipation and outcome.

Primary Performance Endpoint is defined as the completion of imaging required for the study procedure with the NUVISION™ NAV Ultrasound Catheter without resort to non-study ultrasound device(s).

The number of subjects who successfully completed the procedure without resort to a non-study ultrasound device will be summarized overall and per procedure type (atrial ablation/ventricular ablation) for the PP Analysis Set.

A listing of the primary performance endpoint will be provided.

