15.2.2 Relationship to Study Device

For all collected AEs, the clinician who examines and evaluates the participant will determine the AEs causality based on temporal relationship and his/her clinical judgment. The degree of certainty about causality will be graded using the categories below as described per Medical Device Regulation (MDR)

Table 4: Adverse Event Causality Classifications

Caused By	Relation	Definition of Relation
Device	Definitely (Causal Relationship)	The event is associated with the investigational device beyond reasonable doubt
	Probable	The relationship with the use of the investigational device seems relevant and/or the event cannot be reasonably explained by another cause, but additional information may be obtained
	Possibly	The relationship with the use of the investigational device is weak but cannot be ruled out completely. Cases where relatedness cannot be assessed, or no information has been obtained should also be classified as possible
	Not related	Relationship to the investigational device can be excluded
Study Procedure	Definitely (Causal Relationship)	The event is associated with the study procedure beyond reasonable doubt
	Probable	The relationship with the study procedure seems relevant and/or the event cannot be reasonably explained by another cause, but additional information may be obtained
	Possibly	The relationship with the study procedure is weak but cannot be ruled out completely. Cases where relatedness cannot be assessed, or no information has been obtained should also be classified as possible
	Not related	Relationship to the procedure can be excluded

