15.4 Reporting Procedures

15.4.1 Adverse Event Documentation and Reporting Requirements

Subjects should be encouraged to report AEs spontaneously or in response to general, non-directed questioning (e.g. “How was your health been since last visit?”). Anytime during the study, the subject may volunteer information that resembles an AE.

Each AE must be reported to the sponsor regardless of classification, seriousness, intensity, outcome or causality. The investigator is responsible for ensuring that all AEs observed by the investigator, or reported by the subject, that occur from the time that the subject has signed the informed consent through the end of the study are properly assessed, recorded, and reported as defined and described in the AEs, Adverse Device Effects and Device Deficiencies section of this protocol (section 0). All AEs must be documented by completing subject’s medical records (source documents) and appropriate eCRF by the investigator or study coordinator throughout the study and provided to the Sponsor. All AEs will be monitored until they are adequately resolved or explained.

Anonymized documentation pertaining to the AE (e.g. laboratory tests, consultation reports, post-mortem reports, new information relating to a previously reported AE, correspondence with the local EC, etc.) will be provided by the investigator to the sponsor or designee in a timely manner, when requested. Follow-up reports relative to the subject’s subsequent course must be submitted to the sponsor or designee until the event has resolved or, in case of permanent impairment, until the condition stabilizes. If the subject is withdrawn from the study because of the AE, the information must be included on the appropriate eCRFs.

The Sponsor is responsible for the classification of AEs and ongoing safety evaluation of the study and shall review the investigator’s assessment of all AEs. The sponsor will determine and document in writing their seriousness and relationship to the investigational device. In case of disagreement between the sponsor and the PIs, the sponsor shall communicate both opinions to the concerned parties.

Biosense Webster will ensure that investigators are instructed to return devices suspected of causing an AE or SAE (i.e., linked to device-related AE) in accordance with relevant regulations and current company procedures.

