15.5 Safety Oversight

Safety oversight will be conducted as described in the Safety Management Plan. Aggregate safety data will be reviewed during enrollment by the study safety lead in order to promptly identify new issues or trends which may have an impact on the conduct of the study and/or subject safety. Under the rules as defined in the Safety Management Plan, safety events will be reviewed by the Safety Management Team which may recommend appropriate action(s) to ensure subject safety.

16. Administrative Responsibilities

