20.4.6 Analysis for Primary Endpoints

Primary Performance Endpoint is defined as the completion of imaging required for the study procedure with the NUVISION™ NAV Ultrasound Catheter without resort to non-study ultrasound device(s).

The number of subjects who successfully completed the procedure without resort to a non-study ultrasound device will be summarized overall and per procedure type (atrial ablation/ventricular ablation) for the PP Analysis Set.

A listing of the primary performance endpoint will be provided.

Primary Safety Endpoint is defined as the occurrence of serious adverse events related to the Investigational catheter within 7 days of index procedure. An SAE will be counted as related to the investigational catheter if the relationship to a study catheter is anything other than 'Not Related'.

The number of subjects with SAEs related to the investigational catheter will be summarized in the Safety Analysis Set overall and per procedure type (atrial ablation/ventricular ablation) by System Organ Class and Preferred Term and level of relationship. All tables will present summaries both by subject and by event. If a subject has multiple occurrences of an event within a level of summarization, then for the by-subject summaries only a single occurrence will be counted at each level of summarization at the highest level of severity/relationship; for the by-event summary all events will be counted.

All investigational catheter related SAEs will be listed by System Organ Class and Preferred Term, severity, causality (defined as possible, probable or having a causal relationship to the device and/or procedure), anticipation and outcome.

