24.1.1 Data Collection

eCRFs will be used to collect all subject data during this clinical investigation. eCRFs have been developed to capture the information outlined in this clinical investigation Plan. Modification to the eCRF will only be made if deemed necessary by the sponsor. Data on these eCRFs will be monitored (source verified) and the monitor will ask the site representative to correct if necessary, to match the source documents. All changes made to the data will be tracked in the electronic audit trail. The investigator will be required to sign designated eCRFs as verification that they have been reviewed and the data entered are correct. Data from these eCRFs will be used to provide analysis of this clinical investigation.

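### Must the plan name whose rating of seriousness and device relationship decides the primary safety endpoint?

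*SAP*

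**What the plan says.** Protocol 20.4.6 and SAP 8.5 define relatedness for the primary safety endpoint by one sentence: "An SAE will be counted as related to the investigational catheter if the relationship to a study catheter is anything other than" *not related*. Neither text names a rater.

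Two parties give an opinion. Under Protocol 15.2.2, "the clinician who examines and evaluates the participant will determine the AEs causality based on temporal relationship and his/her clinical judgment", using the four-level scale of Table 4. Under Protocol 15.4.1 the sponsor reviews the investigator's assessment, and "The sponsor will determine and document in writing their seriousness and relationship to the investigational device". For conflicts the same section says: "In case of disagreement between the sponsor and the PIs, the sponsor shall communicate both opinions to the concerned parties".

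Two other provisions bear on the point. Protocol 24.1.1 states: "Data from these eCRFs will be used to provide analysis of this clinical investigation". Protocol 15.5 states: "Safety oversight will be conducted as described in the Safety Management Plan". That plan is not among the documents.

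**The concern.** An endpoint built on a judgement should normally have one identified source for it. Here two parties are each told to determine device relationship, the protocol foresees that they may differ, and it requires only that both views be passed on. The statistical text has a rule about taking the highest category ("only a single occurrence will be counted at each level of summarization at the highest level of severity/relationship"), but it deals with repeat occurrences within a subject, not two opinions on one event.

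The study is open-label, single-arm and first-in-human. If the source of the rating were chosen once an event was known, the choice could decide whether the report shows no related SAE or one. The shift could go either way, because the sponsor may also upgrade an event. Disagreement is plausible: the cut lies between *possibly* and *not related*, and during an ablation it can be hard to separate a catheter effect from a procedure effect.

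**Working it through.** The plan gives no rate or interval to reproduce; the sample size rests on earlier experience, not on a formula. The check has three parts.

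**1. Which rating do the documents point to?**

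- Protocol 24.1.1 makes the eCRF the source for analysis, and Protocol 15.4.1 has the investigator or study coordinator complete the eCRF for each adverse event. This points to the site's rating.
- The causality levels to be listed under SAP 8.5 (possible, probable, causal; for device and/or procedure) are those of Table 4, the clinician's scale. Protocol 15.4.1 has the sponsor rate relationship to the device only, so a listed procedure causality can only be the clinician's.
- No section says that the sponsor's determination is held in the study database.
- Against this, Protocol 15.4.1 also makes the sponsor responsible for classifying adverse events.
- For seriousness, only the sponsor is expressly told to determine it. A site rating is implied by the SAE reporting duties (Table 7) and by the sponsor's review of the investigator's assessment.

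The investigator's eCRF rating is the natural reading for relationship. That is an inference, not a stated rule.

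**2. Where does an event go if the ratings differ?**

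| Raters differ on | Under one rating | Under the other |
|---|---|---|
| Relationship of a serious event | Primary safety endpoint | Other SAEs, secondary (Protocol 20.4.7, SAP 8.6) |
| Seriousness of a related event | Primary safety endpoint | Related non-serious AEs, secondary (same sections) |
| Both | Primary safety endpoint | Listing of unrelated non-serious AEs (Protocol 20.4.8, SAP 8.7) |

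In every row the event is reported somewhere.

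**3. How large is the shift?**

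Inputs: n = 30 (Protocol 20.2, SAP 7), assuming all are in the Safety Analysis Set; two-sided 95% level (SAP 5); one discordant event (assumed). The intervals are exact Clopper-Pearson and are added here for scale; the text for this endpoint plans counts and names no interval.

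- x = 0: lower limit 0; upper limit 1 − 0.025^(1/n). For n = 30: 1 − 0.025^(1/30) = 11.6%.
- x = 1: lower limit 1 − 0.975^(1/n); upper limit is the p that solves (1 − p)^n + n·p·(1 − p)^(n−1) = 0.025. For n = 30: 0.1% and 17.2%, around 1/30 = 3.3%.

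Results are also given by procedure type, for which the documents state no split. Stratum sizes of 15 and 10 are assumptions:

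| n | 0 events | 1 event |
|---|---|---|
| 30 | 0% (0 to 11.6%) | 3.3% (0.1 to 17.2%) |
| 15 | 0% (0 to 21.8%) | 6.7% (0.2 to 31.9%) |
| 10 | 0% (0 to 30.8%) | 10.0% (0.3 to 44.5%) |

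The overall intervals for 0 and 1 events overlap from 0.1% to 11.6%.

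**The case for a change.** The best case for a change is that it costs little. One sentence in each document would remove any suspicion that the rater was chosen after the event. Counting an event if either party calls it related would stop a downgrade by one party from removing it. Zero versus one related SAE is the figure readers of a first-in-human report look at first, and Protocol 20 says it sets out all analyses and details.

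Some of this stands: the rater is not named, and naming one would be tidier. But the either-rater rule is a preference on which statisticians could reasonably differ; naming one rater, or citing the Safety Management Plan if it holds a rule, would serve equally well. It cannot be said that readers would be unable to see a disagreement: the listings include causality, but the shells are not given (SAP 9 is a placeholder), so the number of columns is unknown.

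The room for an unseen switch is also limited. Table 4 sends unassessable cases to *possibly*, so only a dispute over whether a link can be excluded matters. The sponsor must record its determination in writing and pass on both opinions, and eCRF changes leave an audit trail.

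**Conclusion.** No change is needed. Protocol 20.4.6 and SAP 8.5 leave out a detail that an analyst can fill sensibly: use the investigator's rating from the eCRF and report any event on which the sponsor's written determination differs. Either rating gives a valid descriptive count. Both documents exclude hypothesis testing, set no success criterion and make no clinical claims, so no decision depends on the choice.

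The effect is one subject in 30, or 3.3 percentage points, for each subject whose classification turns on a disputed rating. It is larger within a procedure type (6.7 points if 15 subjects, 10.0 if 10). This assumes that 30 subjects are analysed and that a discordant SAE occurs at all; the documents give no basis for how likely that is. The reading that the investigator's rating is used is firmer for relationship than for seriousness, and the Safety Management Plan, unseen here, may already settle both.
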